9.2.6. Potential Hy's Law

Criteria for potential Hy's law cases are as follows:

- ALT or AST $\geq 3 \times$ ULN AND
- Total bilirubin $\geq 2 \times$ ULN AND
- Alkaline phosphatase $< 2 \times$ ULN

Study site personnel must report every participant who meets these potential criteria. Typically, all 3 analytes will be obtained from the same sample, but they may come from multiple samples taken within a 24-hour period. This requirement applies from the time the participant signs the ICF for the study until 30 days after the final protocol-defined study visit or the last known dose of study treatment (if the final visit does not occur).

A laboratory alert for potential Hy's law cases will be in place, and must notify investigators and the sponsor immediately when the above criteria have been met. A potential Hy's law case must be faxed or e-mailed to the sponsor on an adverse event of interest form, as soon as possible (within 24 hours of learning of the potential Hy's law case) to the SAE fax number or e-mail shown on the title page of this protocol, even if no AE has occurred. The eCRF for potential Hy's law cases must be completed within 7 calendar days. Every effort to determine the cause of the liver enzyme abnormalities must be made, and close monitoring should be initiated in conjunction with the medical monitor and in accordance with the FDA Guidance for Industry, Drug-Induced Liver Injury: Premarketing Clinical Evaluation, [July 2009](#).

9.2.7. Medication Errors

Medication error refers to any unintended error in the dosing and/or administration of the study treatment as per instructions in the protocol. Medication errors generally fall into 4 categories as follows:

- Wrong study drug
- Wrong dose (including dosing regimen, strength, form, concentration, amount)
- Wrong route of administration
- Wrong participant (ie, not administered to the intended participant)

Medication errors include occurrences of overdose and underdose of the study treatment. For Part B, participants should be instructed as described in Section [7.2](#) (Dose Modification) for missed doses.

9.3. Treatment of Overdose

AGN-241751 has a short half-life; hence, even in the event of an overdosage, the likelihood of lasting high exposures would be minimal. Although not observed within healthy volunteers receiving 50 mg of AGN-241751 for 10 consecutive days, minimal liver findings have been

observed in toxicology studies within the dog. Part B safety laboratory tests, including AST and ALT, will be performed at Visit 9 (Day 7), Visit 12/ET (Day 14/ET), and Visit 14 (Day 21) (Safety Follow-Up) to monitor participants should dosing errors occur. Unscheduled safety assessments may be performed as clinically indicated at any time during the study at the discretion of the investigator.

9.4. Safety Assessments

Planned timepoints for all safety assessments are provided in the schedule of activities (Section 2.1 and Section 2.2). In addition, unscheduled assessments of vital signs, clinical laboratory tests, and ECGs may be performed as clinically indicated at any time during the study at the discretion of the investigator.

9.4.1. Physical Examinations

A complete physical examination will be performed at Screening and at Visit 6/ET (Part A) or at Screening and Visit 12/ET (Part B) by a professionally trained physician or health professional listed on Form FDA 1572 and licensed to perform physical examinations.

9.4.2. Vital Signs

Vital signs (pulse rate, systolic and diastolic blood pressure, oral or tympanic temperature, and body weight) will be assessed at every visit (Part A) and at Screening, Baseline (Day -1), 4 hours postdose at Visit 3 and Visit 10/Discharge (Day 8), Visit 12/ET (Day 14/ET), and Visit 14 (Day 21) (Part B). Height will be assessed at Screening only in both parts of the study.

Blood pressure and radial pulse rate will be measured in the supine position followed by the standing position. The standing measurements should be assessed after a sufficient amount of time (approximately 1 to 3 minutes) has been elapsed to allow the BP to equilibrate in the standing state.

Radial pulse rate should be measured after blood pressure measurements. Blood pressure may be measured manually or by machine, but radial pulse rate should only be measured manually and for a sufficient time to acquire an accurate measurement.

Participants should be instructed not to wear clothing with tight sleeves when they come for clinic visits. Additionally, participants should be kept as calm and undisturbed as possible while blood pressure and pulse rate measurements are taken (eg, there should be no talking while the blood pressure is being measured). The same arm and blood pressure cuff (appropriate to the arm circumference) should be used for all blood pressure measurements.

Whenever possible, the participant's weight will be measured at the same time of day; participants should wear their usual indoor clothing, but take off their jacket and shoes. For each participant, body weight should be determined using the same equipment during the study after ensuring its proper calibration.

9.4.3. Electrocardiograms

A 12-lead ECG will be performed at Screening and Visit 6/ET (Part A) and at Visit 1 (Screening), Visit 12/ET (Day 14/ET), and Visit 14 (Day 21) (Part B). ECGs will be performed and electronically transmitted to a central ECG laboratory for analysis according to the instructions provided by the central ECG laboratory. Measurements (in msec) will be recorded for the following parameters: PR interval, QRS duration, and uncorrected QT interval. QTcB (Bazett corrected QT interval) and QTcF (Fridericia corrected QT interval) will be calculated.

The overall interpretation and determination of the clinical relevance of ECG findings using the central ECG interpretation laboratory report will be the responsibility of the investigator and will be recorded in the participant's eCRF.

Throughout the study, the investigator will review the central ECG reports and indicate the clinical significance of all abnormal values, and then sign and file the report in the participant's study file. In case of any abnormal ECG finding, unscheduled ECGs may be conducted at the discretion of the PI.

9.4.4. Clinical Safety Laboratory Assessments

- See [Appendix 2](#) for the list of clinical laboratory tests to be performed and the schedule of activities (Section 2.1 [Part A] and Section 2.2 [Part B]) for the timing and frequency.
- The investigator must review the laboratory report, document this review, and record any clinically relevant changes occurring during the study that are considered Adverse Events per the judgment of the investigator in the AE section of the eCRF. The laboratory reports must be filed with the source documents. Clinically significant abnormal laboratory findings are those which are not associated with the underlying disease, unless judged by the investigator to be more severe than expected for the participant's condition.
- All laboratory tests with values considered clinically significantly abnormal during participation in the study or after the last dose of study treatment should be repeated until the values return to normal or baseline or are no longer considered clinically significant by the investigator.
 - For liver function tests, if a participant has the following, an unscheduled retest should be performed: ALT or AST $\geq 3 \times$ ULN, total bilirubin $\geq 2 \times$ ULN, and/or alkaline phosphatase $< 2 \times$ ULN (see also Section 9.2.6).
 - If such values do not return to normal/baseline within a period of time judged reasonable by the investigator, the etiology should be identified and the sponsor notified.
 - All protocol-required laboratory assessments, as defined in [Appendix 2](#), must be conducted in accordance with the laboratory manual and the schedule of activities.
 - If laboratory values from non-protocol specified laboratory assessments performed at the institution's local laboratory require a change in participant management or are considered clinically significant by the investigator (eg, SAE or AE or dose modification), then the results must be recorded in the eCRF.

9.4.5. Columbia-Suicide Severity Rating Scale

The C-SSRS is an instrument that reports the severity of both suicidal ideation and behavior ([Appendix 12](#) and [Appendix 13](#)). Suicidal ideation is classified on a 5-item scale: 1 (wish to be dead), 2 (nonspecific active suicidal thoughts), 3 (active suicidal ideation with any methods [not plan] without intent to act), 4 (active suicidal ideation with some intent to act, without specific plan), and 5 (active suicidal ideation with specific plan and intent). The C-SSRS also captures information about the intensity of ideation, specifically the frequency, duration, controllability, deterrents, and reasons for the most severe types of ideation. Suicidal behavior is classified on a 5-item scale: 0 (no suicidal behavior), 1 (preparatory acts or behavior), 2 (aborted attempt), 3 (interrupted attempt), and 4 (actual attempt). More than 1 classification can be selected provided they represent separate episodes. For actual attempts only, the actual or potential lethality is classified for the initial, most lethal, and most recent attempts.

For Part A and Part B, the C-SSRS will be completed at all study visits (once per visit; predose at applicable visits) (see [Section 2.1](#) [Part A] and [Section 2.2](#) [Part B]). At Screening, the C-SSRS will be completed for the participant's lifetime history of suicidal ideation and behavior. At all other visits, the C-SSRS will be completed for ideation and behavior since the previous visit. The C-SSRS will be evaluated and signed at each visit by a qualified staff member (ie, the investigator or designee who has extensive professional training and experience in assessing mental illness), before the participant leaves the study center.

9.4.6. Brief Psychiatric Rating Scale—Positive Symptoms Subscale

The BPRS is an 18-item evaluation that assesses psychiatric symptoms and unusual behavior ([Overall and Gorham 1962](#)). The BPRS+ is a subset of the BPRS that assesses 4 components of the BPRS related to the degree of psychosis: Conceptual Disorganization, Suspiciousness, Hallucinatory Behavior, and Unusual Thought Content ([Appendix 10](#)). Only the 4 items of BPRS+ subscale will be collected and analyzed. The BPRS+ will be administered by the investigator or designee with extensive professional training and experience in assessing mental illness. For Part A and Part B, at Screening (Visit 1), the BPRS+ will be administered with a look-back timeframe of 1 week. At all other evaluations, the BPRS+ will be administered with a look-back timeframe of "since last evaluation." The BPRS+ will be completed as specified in the schedule of activities in [Section 2.1](#) (Part A) and [Section 2.2](#) (Part B) (including the designated look-back periods for each BPRS+ administration).

9.4.7. Clinician Administered Dissociative States Scale

The CADSS is a 28-item clinician-administered measure of perceptual, behavioral, and attentional alterations occurring during active dissociative experiences composed of 23 subjective self-reported and 5 objective observer-reported ratings, each scored from 0 (not at all) to 4 (extremely) ([Appendix 11](#)). Only the 23 subjective items will be collected and analyzed. The CADSS provides a validated assessment of dissociative states sensitive to change over time and amenable to repeated measures ([Bremner 1998](#)). The CADSS will be administered by the investigator or designee with extensive professional training and experience in assessing mental illness. For Part A and Part B, at Screening (Visit 1), the CADSS will be administered with a

look-back timeframe of 1 week. At all other evaluations, the CADSS will be administered with a look-back timeframe of “since last evaluation.”

The CADSS will be completed as specified in the schedule of activities in Section 2.1 (Part A) and Section 2.2 (Part B) (including the designated look-back periods for each CADSS administration).

9.5. Pharmacokinetics (Part B Only)

In Part B of this study, collection of a single CSF sample is an optional procedure, as participants may/may not choose to allow this sample collection without impacting their participation in the study. For those participants who agree and have given consent to provide a CSF sample for PK analysis, lumbar puncture will be used to collect CSF, and a maximum of 4 mL of CSF will be collected. Collection of CSF is preferred at Visit 5 (Day 3), but can be done at Visit 4 or Visit 6, either immediately prior to the morning dose or at 8 hours after the morning dose. Within each site, 1 sample per participant will be collected, and study staff will alternate between predose and postdose for participants (eg, 1st participant sample is collected predose, 2nd participant sample is collected postdose, 3rd participant sample is collected predose, etc.). Additional details of the CSF sample collection, handling, and storage are presented in [Appendix 18](#).

Additional exploratory analysis may be performed on collected CSF samples.

9.6. Pharmacodynamics (Part B Only)

9.6.1. Quantitative Electroencephalography and Event Related Potential Assessments and Outputs

In Part B of the study, evaluation of pharmacodynamic endpoints (qEEG/ERP) between AGN-241751 and placebo (double-blinded) will be performed at selected sites using the measures described below.

9.6.1.1. Karolinska Sleepiness Scale

The KSS is a 9-point self-reported scale of subjective assessment of a participant’s level of drowsiness at the time ([Appendix 17](#)). The KSS will be conducted prior to each qEEG measurement to assess for sleep-deficit related differences between qEEG measurements. The scale will control for any sleepiness variations in the qEEG and ERP outputs. The scale will be measured as follows:

- Baseline: Mid-day (approximately 1200 hours), and afternoon (approximately 1700 hours) (window of \pm 2 hours between mid-day and afternoon assessments)
- Day 1: Predose and 4, 8, and 12 hours postdose
- Day 2: 24 hours post Day 1 morning dose (prior to the Day 2 morning dose)
- Day 7: Predose and 4, 8, and 12 hours postdose
- Day 8: 24 hours post Day 7 morning dose (prior to the Day 8 morning dose)

- Day 14
- Day 21

Error windows permitted for the KSS measurements will be \pm 30 minutes at any collection timepoint up to 12 hours postdose and \pm 1 hour at any collection timepoint up to 24 hours postdose.

9.6.1.2. Event-Related Potential and Electroencephalography Measurements

The qEEG and ERP are noninvasive tests that analyze the electrical activity of the brain using data from surface electrodes in contact with 19 or more areas of the scalp. Engagement of the NMDA receptor by AGN-241751 is expected to result in measurable changes in qEEG and ERP data.

Prior to the qEEG assessments on Day –1, each participant will undergo a hearing test to ensure detection of the stimuli used for the ERP assessments. Should a participant not be able to detect the planned stimuli, the intensity of the stimuli may be adjusted accordingly.

The qEEG will be measured as follows:

- Baseline: Mid-day (approximately 1200 hours), and afternoon (approximately 1700 hours) (window of \pm 2 hours between mid-day and afternoon assessments)
- Day 1: Predose and 4, 8, and 12 hours postdose
- Day 2: 24 hours post Day 1 morning dose (prior to the Day 2 morning dose)
- Day 7: Predose and and 4, 8, and 12 hours postdose
- Day 8: 24 hours post Day 7 morning dose (prior to the Day 8 morning dose)
- Day 14
- Day 21

Error windows permitted for the qEEG measurements will be \pm 30 minutes at any collection timepoint up to 12 hours postdose and \pm 1 hour at any collection timepoint up to 24 hours postdose. Test times should not be confounded by food intake; eg, if baseline is done 30 minutes after lunch, the test should be 30 minutes after lunch.

The ERPs will be measured approximately 10 minutes following each corresponding qEEG measurement.

qEEG and ERP Assessments and Outputs

At the times specified above, a 5-minute resting qEEG with eyes closed, a 5-minute resting qEEG with eyes open, a 10.5-minute MMN task ([Appendix 20](#)) and a 10.5-minute ASSR task ([Appendix 20](#)) will be performed with participants seated comfortably in a sound-attenuated room. In addition to 19 qEEG leads according to the international 10/20 system, vertical and horizontal EOGs will be recorded. The reference electrode will be left mastoid (A1) with ear lobe (A2) recorded as an active lead. Digital referencing to linked ears will be done off-line. An

additional electrode on the nose (Nz) is required for accurate identification of the MMN. The resting qEEGs will be evaluated by means of spectral analysis, coherence analysis, and frequency analysis. After artifact rejection or correction, the mean absolute amplitude spectra (square root of power spectral density function) will be computed. The primary qEEG endpoints will be changes from predose baseline in the absolute spectral amplitudes in 1 Hz bands from 1.0 to 50.0 Hz. Secondary measures will include changes from predose baseline in the absolute spectral amplitudes and magnitude squared coherences in various clinical bands (Delta [1.0 - 4.0 Hz], Theta [4.0 - 8.0 Hz], Alpha [8.0 - 12.0 Hz], Beta [12.0 - 25.0 Hz], Hi-Beta [25.0 - 30.0 Hz], Gamma [30.0 - 50.0 Hz], Alpha 1 [8.0 - 10.0 Hz], Alpha 2 [10.0 - 12.0 Hz], Beta 1 [12.0 - 15.0 Hz], Beta 2 [15.0 - 18.0 Hz], Beta 3 [18.0 - 25.0 Hz], Gamma 1 [30.0 - 35.0 Hz], Gamma 2 [35.0 - 40.0 Hz], Gamma 3 [40.0 - 50.0 Hz]; coherence in these bands) and derived frequency measures. Additional secondary endpoints will include coherences and derived frequency measures, for each of which the endpoints will be changes from predose baseline values. Magnitude squared coherence will be measured for specific pairwise combinations of the 19 qEEG electrodes in the same clinical bands. These pairs will capture the relevant inter- and intra-hemispheric coherences and will include F3-F4, C3-C4, P3-P4, O1-O2, F3-P3, and F4-P4. Derived frequency analysis will consist of computing the dominant frequency in the range of 6.0 to 12.5 Hz, the ASI, and the TBR.

Each ERP task will be assessed in sequential multiple blocks. For the MMN task, the assessment will be done using deviant stimuli differing in pitch from standard stimuli. For the ASSR task, the assessment will be done using stimulus rates of 30/s and 40/s.

Each ERP task will yield several measurements, which will serve to compute primary ERP endpoints. For the MMN task, the components include P50, N100, and P200 for the standard and deviant stimuli, and the MMN, which derives from a difference of deviant-standard ERPs. For all ERP components, measures of peak latency, peak amplitude, and average amplitude (AUC) will be computed and analyzed for change with respect to predose baseline. Baseline-adjusted ERP component measures will serve as endpoints for statistical analysis. The primary ASSR measure is the peak-to-peak amplitude of the sustained portion (latency > 150 ms) of the ASSR in the time domain. Secondary measures include the averaged wavelet magnitude and inter-trial phase coherence ([Appendix 20](#)). Baseline-adjusted ASSR measures will serve as endpoints for statistical analysis.

For all qEEG and ERP endpoints, the baselines for computing changes at each postdose timepoint will be the mean of the 3 baseline values on Day -1 (mid-day), Day -1 (afternoon), and Day 1 (predose). Change scores will be computed as normalized differences $((V(t) - V(b)) / (V(t) + V(b)))$, where $V(b)$ is the value at mean baseline and $V(t)$ is the value at a specific timepoint. Other change metrics may also be examined, such as simple differences from baseline and simple ratios of postdose to baseline values, as these provide different levels of control for baseline variation. The change metric that shows the greatest sensitivity to changes without introducing excessive bias will be selected for formal analyses of variance.

9.7. Genetics

For Part A, randomized participants may consent to participate in the genetic analysis component of the study. For those randomized participants who agree, the consent may be collected at any time prior to collection of the sample. For Part B, if participants consent to this sampling and are randomized, the sample will be collected predose at Visit 9 (Day 7).

For both Part A and Part B, for those who consent and are randomized, a 4 mL sample for DNA isolation will be collected at any time during the study after the consent has been signed (Part A) or at Visit 9 (Day 7) (Part B). With the samples, polymorphisms within the NMDA receptors may be assessed to understand treatment response to AGN-241751. Additional exploratory assessments may also be conducted from DNA collected within these samples. Participation is optional. Participants who do not wish to participate in the genetic research may still participate in the study. Participant confidentiality will be maintained at all times.

9.8. Biomarkers

Biomarker samples are not being collected within this study.

9.9. Medical Resource Utilization and Health Economics

Medical resource utilization and health economics parameters are not evaluated in this study.

10. Statistical Considerations

10.1. Sample Size Determination

10.1.1. Part A

The sample size of approximately 25 randomized participants in each of the 4 treatment groups is not based on statistical power consideration due to the lack of information of AGN-241751 for the variability of change from baseline to 1 day after first dose in MADRS total score.

10.1.2. Part B

In Part B of the study, the sample size of approximately 40 randomized participants in each of the 3 treatment groups is not based on statistical power consideration since this is an exploratory study.

10.2. Populations for Analyses

10.2.1. Part A

The analysis populations will consist of participants as defined below:

- The mITT population includes all randomized participants who received at least 1 administration of study treatment, and have a baseline MADRS total score and at least 1 postbaseline assessment for the MADRS total score during the double-blind treatment period. Participants will be summarized according to the randomized study treatment.
- The safety population includes all participants who received ≥ 1 administration of study treatment. Participants will be summarized according to the study treatment they actually received.

10.2.2. Part B

The analysis populations in Part B will consist of participants as defined below:

- The mITT population includes all randomized participants who received at least 1 administration of study treatment and have a baseline MADRS total score and at least 1 postbaseline assessment for the MADRS total score during the double-blind treatment period. Participants will be summarized according to the randomized study treatment.
- The safety population includes all participants who received ≥ 1 administration of study treatment. Participants will be summarized according to the study treatment they actually received.
- The PD population includes all randomized participants who received ≥ 1 administration of study treatment and have Day -1 qEEG and ERP assessments and at least 1 postbaseline assessment for the qEEG and ERP assessments during the double-blind treatment period. Participants will be summarized according to the randomized study treatment.
- The PK population includes all randomized participants who received ≥ 1 administration of study treatment and have at least 1 CSF collection in Part B. Participants will be summarized according to the randomized study treatment.

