10.3.4. Pharmacodynamic Analysis (Part B Only)

Analysis of the qEEG and ERP assessments will be performed using the PD population for the double-blind treatment period. Initial details of the analysis of the qEEG and ERP data are described in [Appendix 20](#), but will be fully defined in a PD SAP.

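### The Part B PD population requires both qEEG and ERP, so a participant who lacks one measure is dropped from the analysis of the other; the loss is probably small

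*Protocol*

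**What the plan says.** Protocol section 10.2.2 (Part B) limits the PD population to randomized, dosed participants with both qEEG and ERP on Day -1 and "at least 1 postbaseline assessment for the qEEG and ERP assessments during the double-blind treatment period". Section 10.3.4 then states: "Analysis of the qEEG and ERP assessments will be performed using the PD population for the double-blind treatment period". No section of the supplied documents defines a separate set for either measure.

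The two measures are distinct. Section 4.2 lists change in qEEG parameters and change in ERP parameters as separate endpoints. Section 9.6.1.2 describes two 5-minute resting qEEG recordings and two 10.5-minute auditory tasks, and says of the timing: "The ERPs will be measured approximately 10 minutes following each corresponding qEEG measurement".

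For both measures, section 9.6.1.2 says that the baseline for change scores "will be the mean of the 3 baseline values on" Day -1 mid-day, Day -1 afternoon and Day 1 predose. It gives no rule for a participant with fewer than three.

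The PD work "will be performed at selected sites using the measures described below" (section 9.6.1). The number of participants at those sites is not stated. Section 10.3.4 leaves the full definition of the analysis to a PD SAP, which is not among the supplied documents; the supplied SAP covers Part A only.

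**The concern.** Nothing in the resting qEEG endpoints depends on ERP data. The ERP tasks have requirements of their own: the participant must hear the stimuli, and the mismatch negativity needs an additional nose electrode. One measure can therefore be missing while the other is complete. Under the joint rule, that participant contributes nothing to either analysis.

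What is at stake is precision in a subset already limited to selected sites. The mITT rule in the same section is tied to the measure that it serves (MADRS); the PD rule is not.

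A second, smaller matter is that the population rule and the baseline rule do not fit together. One names Day -1 only; the other averages Day -1 and Day 1 recordings.

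**Working it through.** The plan states no PD sample size, power or failure rate, so there is no figure to reproduce. The check is first one of logic, then of scale.

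**Who is excluded.** Sections 10.2.2 and 10.3.4, read together, give:

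- qEEG present on Day -1 and postbaseline, ERP absent on Day -1: excluded from both analyses, although qEEG is intact.
- qEEG present on Day -1 and postbaseline, ERP absent at every postbaseline session: the same.
- The two reverse cases: excluded, although ERP is intact.

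The postbaseline clause could be read loosely as one assessment of either type. The Day -1 clause would still require both.

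**How many chances a participant has.** Section 9.6.1.2 schedules two Day -1 sessions. The double-blind postbaseline sessions are Day 1 at 4, 8 and 12 hours (3), Day 2 (1), Day 7 predose and at 4, 8 and 12 hours (4), Day 8 (1) and Day 14 (1): 3 + 1 + 4 + 1 + 1 = 10. The postbaseline clause excludes only if one measure is absent at all ten, so the Day -1 clause is the one likely to bind.

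**Effect on precision.** If a share x of PD participants is lost from the intact measure, the standard error rises by 1/sqrt(1-x) - 1, whatever the size of the subset:

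- x = 1%: 1/sqrt(0.99) - 1 = 0.5%
- x = 5%: 1/sqrt(0.95) - 1 = 2.6%

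With 40 per arm as the upper bound (section 10.1.2), these shares are 0.4 and 2 participants per arm.

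**What x might be.** Let p be an assumed chance that one measure is missing at a session. If one Day -1 session satisfies the rule and sessions fail independently, the Day -1 loss is p². The chance of missing all ten later sessions, p to the power 10, is negligible.

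| p (assumed) | x = p² | Rise in SE |
|---|---|---|
| 5% | 0.25% | 0.1% |
| 10% | 1% | 0.5% |
| 15% | 2.25% | 1.1% |

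If failures persist within a participant, x moves from p² towards p; at p = 5% the rise then lies between 0.1% and 2.6%. Section 10.2.2 does not say whether one or both Day -1 sessions are needed. If both were, x would be 1 - (1-p)², which at p = 5% is 9.75%, and the rise would be 1/0.95 - 1 = 5.3%.

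**Population rule against baseline rule.** Two cases show the mismatch:

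- Day -1 recordings present, Day 1 predose missing: meets 10.2.2, but the three-value mean in 9.6.1.2 cannot be formed.
- Day 1 predose present, Day -1 missing: excluded by 10.2.2, although 9.6.1.2 uses that recording as one of its three components.

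**The case against.** The strongest reply is that the rule is a legitimate choice with little effect. The schedule of activities treats KSS, qEEG and ERP as one procedure, each ERP is tied to its own qEEG, and a common set gives one denominator. The rule asks that assessments exist and sets no quality threshold, so an artifact-laden recording need not exclude anyone. Some causes of ERP failure are already addressed: a Day -1 hearing test with adjustable stimulus intensity, and hearing loss as an exclusion (criterion 29). These are additional endpoints in a part described as exploratory, and the PD SAP may refine the definition. All of this stands as a limit on the size. It does not change what 10.2.2 says, and no supplied document corrects it.

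Three stronger readings are tempting, and the documents do not support them:

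- **That the rule discards a valid Day 1 predose baseline.** Section 9.6.1.2 defines baseline as a mean of three values, two of them from Day -1. One morning recording is not that baseline, and accepting it alone would change the construct.
- **That the loss is likely to differ by arm.** Randomization takes place at Visit 3 on Day 1 (section 5.1.2), so Day -1 loss cannot be caused by treatment. Loss through the postbaseline clause needs all ten sessions of one measure to be missing, and nine of the ten fall within the inpatient stay.
- **That the loss is large.** No failure rate is given, and the number of sessions argues against it.

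**Conclusion.** The point holds as one of definition. The joint rule, applied through a single analysis set, removes intact qEEG data when ERP is absent on Day -1 or at every postbaseline session, and the reverse. The effect is on precision only and is probably small: a 0.5% rise in standard error if 1% of PD participants are affected, 2.6% if 5% are. Both shares are assumptions. The judgement that the loss is small also assumes that one Day -1 session satisfies the rule; the wording leaves this open. The MADRS analyses use the mITT population and are not touched. The mismatch between the Day -1 requirement and the three-value baseline is real whatever the failure rate, and it needs a rule. The PD SAP was not available and could settle both points. This is a minor improvement that is easy to make.

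**What to change.** In section 10.2.2 and the PD SAP, replace the single PD population with two sets: qEEG-evaluable and ERP-evaluable. Each should require a baseline recording and at least one double-blind postbaseline recording of that same measure. Section 10.3.4 should name the set for each analysis.

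Separately, reconcile 10.2.2 with 9.6.1.2. State whether one or both Day -1 sessions are required, and how the baseline is formed when one or two of the three recordings are missing. Any use of Day 1 predose alone as baseline should be a sensitivity analysis, because it replaces a mean that includes mid-day and afternoon values with a single morning one.

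The cost is a few lines of text and two slightly different denominators in the PD tables. No additional data collection is needed.
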